**DESIGN: Randomized Control Trail**

**DATA COLLECTION PROCEDURE:**

After screening of more than 50 MI patients 26 stable post MI patients both males and females on the basis of inclusion and exclusion criteria were enrolled. After enrollment final step for inclusion in study was 6 minute walk test. All patients performed treadmill 6 minute walk test. Patients that successfully completed initial 3 min of walk test were included in the study. Informed consent was signed by all patients as an agreement to participate in research. Total patients at end of study was 26 with drop outs of 4 .After enrollment in study 1st day was pre assessment day.1st step was selection in either control or experimental group. Lottery method was used for random allocation of patients. Self structured questionnaire was filled that included demographics, patient past medical, surgical, drug history, comorbidites, risk stratification. Basic baseline evaluation was done that included ECG, urea, creatinine, lipid profile. Pre echocardiography of all patients was done Pre MAC New QLMI was filled by examiner herself. After completion of all pre assessment exercise session of the patient was started from next session. Total weeks of treatment session were 6. Exercise was performed 3 times a week on alternating days. Total days of exercise were 18. Before treatment session proper warm up for 15 minutes was done Pre vitals including heart rate, BP, Respiratory rate, SpO2 was recorded. Karvonens formula was used to calculate 60-80% of target heart rate in all patients .The goal of exercise was to reach target heart rate. Emergency trolley consisting of major life saving drugs was available that included (Angisid, Injection Atropine, Adrenaline, Heparin, Lignocaine, Streptokinase, Nitroglycin, Normal Saline, Glucose) plus examiner was qualified in ACLS. Patient speed was increased gradually from first to six weeks depending on each patient target heart rate. Likewise weight in quadriceps resistive exercise and hand grippers were increased gradually with number of repetitions remaining same. Rating of perceived exertion and fatigue scale was used to mark patient dyspnea and fatigue level. Patients in control group were given standard aerobic interval treatment while patient in experimental group was given aerobic plus resistance interval treatment. During session continuous vital monitoring was done using saturation probe and cardiac monitor. After completion of session post vitals HR, BP, RR, Spo2 RPE and fatigue Cool down exercises were performed to stabilize patient. After completion of total 6 weeks of intervention patients post tests were done that included Echocardiography, lipid profile post and Mac New QLMI.

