## DATA ANALYSIS PROCEDURE:

All the patients were assessed at the baseline before the intervention and at the completion of the study. Data was analyzed by using IBM SPSS 21 (Statistical Package for Social Sciences) and expressed in the form of tables and graphs.

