## CURVES OF NORMALITY

[figure not shown]

Figure 4: Normality test (histograms) for Baseline Vitals, A: Heart rate, B: Respiratory rate, C: Saturation, D: Systolic BP, E: Diastolic BP

We applied normality test on Baseline vitals. Histogram showed abnormally skewed curves for Heart rate, respiratory rate and oxygen saturation ( $p=0.000, 0.030, 0.004$ ) respectively and normally skewed curves for systolic and diastolic BP ( $p=0.396$  and  $0.108$ ) respectively. Test of choice is non-parametric, Mann-Whitney U test for the comparison between groups (sample size  $< 30$  in each group).

[figure not shown]

Figure 5: Normality test (histograms), A: Ejection Fraction

We applied normality test on baseline ejection fraction. Histogram showed abnormally skewed curve for ejection fraction ( $p=0.001$ ). Test of choice is non-parametric, Mann-Whitney U test for the comparison between groups (sample size  $< 30$  in each group.)

[figure not shown]

Figure 6: Normality test (histograms), A: Cholesterol, B: Triglycerides

We applied normality test on baseline cholesterol and triglycerides. Histogram showed abnormally skewed curves for cholesterol and triglycerides ( $p=0.000, 0.026$  respectively). Test of choice is non-parametric, Mann-Whitney U test for the comparison between groups (sample size  $< 30$  in each group)

[figure not shown]

Figure 7: Normality test (histograms) for Baseline Quality of life, A: Emotional state, B: Physical state, C: Social state

We applied normality test on baseline quality of life including its three domains of emotional, physical and social state. Histogram showed abnormally skewed curve for emotional ( $p=0.025$ ) and normally skewed curves for physical and social state ( $p=0.129$  and  $0.577$  respectively). Test of choice is non-parametric, Mann-Whitney U test for the comparison between groups (sample size  $< 30$  in each group.)

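### Outcome tests are linked to completing the 6-week programme, with no provision for allocated patients who stop exercising, so a completers-only comparison is likely and cannot be ruled out

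*Combined protocol and SAP*

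**What the plan says.** All statements are in the Combined protocol and SAP.

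- **Outcome timing** (Data Collection Procedure): "After completion of total 6 weeks of intervention patients post tests were done that included Echocardiography, lipid profile post and Mac New QLMI". No other section schedules a post-baseline echocardiogram, lipid profile or MacNew.
- **Course length** (same section): "Total weeks of treatment session were 6" and "Total days of exercise were 18".
- **Patient flow** (same section): "26 stable post MI patients both males and females on the basis of inclusion and exclusion criteria were enrolled", and later "Total patients at end of study was 26 with drop outs of 4".
- **Allocation** (same section): "Lottery method was used for random allocation of patients". The ratio and arm sizes are not given.
- **Who was assessed** (Data Analysis Procedure): "All the patients were assessed at the baseline before the intervention and at the completion of the study".
- **Analysis** (Curves of Normality): "Test of choice is non-parametric, Mann-Whitney U test for the comparison between groups".

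The supplied text has no assessment for a patient who has stopped the sessions, no definition or date of dropout, no analysis population and no method for missing outcomes. The Figure 2 flow chart is not shown and may bear on some of this.

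**The concern.** The lottery protects the comparison only if the patients it allocated are the patients measured and analysed. Here the outcome tests are described as following completion of the exercise course, and nothing separates stopping exercise from leaving the study. An echocardiogram, a blood sample and a questionnaire can all be obtained from someone who no longer attends sessions, so the link is avoidable.

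Patients may stop an exercise course after infarction because of breathlessness, fatigue, low motivation or a cardiac event. These reasons are plausibly related to ejection fraction and MacNew score. The arms also do different sessions (Control Group and Interventional Group sections), so stopping could differ between them. If it does, the remaining patients are no longer the groups that the lottery formed, and a difference can appear without any treatment effect.

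**Working it through.** **1. Figures in the plan.** The session count reproduces: 3 per week × 6 weeks = 18. The patient flow does not: 26 enrolled less 4 lost is 22, and 26 at the end plus 4 lost is 30. Both cases are carried forward. The share possibly without an outcome is 4/30 = 13.3% or 4/26 = 15.4%, if the losses came after allocation. The plan gives no sample size calculation, alpha, SD or effect size to reproduce.

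**2. Average bias.** Assumptions, none from the documents: equal arms of 13 (26 entered), no true effect, standard normal outcome, and correlation r between the tendency to stop and a poor outcome. In each arm the k patients lowest on that tendency are lost.

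The expected four lowest values among 13 standard normals are −1.668, −1.164, −0.850 and −0.603. Losing k patients raises the mean of the remaining 13 − k by r × (sum of the k absolute values)/(13 − k).

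- 4/0: r × 4.285/9 = 0.476r, which is 0.24 SD at r = 0.5 and 0.48 SD at r = 1.
- 3/1: r × (3.682/10 − 1.668/12) = r × (0.368 − 0.139) = 0.229r, which is 0.11 SD and 0.23 SD.
- 2/2: the shifts cancel, so there is no average bias.

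**3. False-positive rate.** Simulation under the same assumptions, with 10,000 replicates per scenario and an exact two-sided Mann-Whitney test at an assumed 5%:

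| Split of the 4 | r = 0.5 | r = 1 |
|---|---|---|
| 4/0 | 7-8% | about 20% |
| 3/1 | about 5% | about 11% |
| 2/2 | about 5% | about 8% |

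The 2/2 excess at r = 1 is not a shift in one direction. It arises because cutting off the lowest values within each arm breaks the independence that the test assumes. With 15 per arm (30 entered), a 4/0 split gives 0.21 and 0.42 SD, with 8% and 20% false positives.

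**4. Fragility of one result.** Assume 15 per arm and use the normal approximation z = (U − n₁n₂/2)/√(n₁n₂(n₁+n₂+1)/12).

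- All 4 lost from one arm: completers 11 v 15 with U = 121 give z = (121 − 82.5)/19.27 = 2.00, p = 0.046. With the 4 restored at the worst ranks, U stays at 121 and z = (121 − 112.5)/24.11 = 0.35, p = 0.72.
- Lost 2 and 2: completers 13 v 13 with U = 123 give z = (123 − 84.5)/19.5 = 1.97, p = 0.048. Restored at the worst ranks, U = 123 + 13×2 + 0.5×2×2 = 151 and z = (151 − 112.5)/24.11 = 1.60, p = 0.11.

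Worst ranks are an extreme placement. They show how much four patients can matter at this size, not what happened.

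**The case against.** A reader might infer that the plan has a completers-only rule and that anyone who stopped certainly yields no outcome. The documents do not support that.

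- **Time point or condition.** The sentence on post tests is a past-tense account of when tests took place. It can be read as the end of week 6, and it does not say that patients who stopped were left untested or that all 18 sessions had to be attended. This stands. Under either reading, though, the rule for a patient who stops is absent.
- **All patients assessed.** The Data Analysis Procedure refers to completion of the study, not of treatment, and on the time-point reading the two sections agree. This prevents stating the problem as fact. It does not remove it, because the text does not say whether all includes the four dropouts.
- **When the four left.** The dropout sentence comes before the lottery is described, and a walk test screened patients after enrolment. Losses before allocation would not bias the randomised comparison. But the same sentence gives the total at the end of the study, so the timing is open.
- **Size.** If the four fell at random across arms of 13, a 4/0 split has probability 2 × 715/14,950 = 10%, 3/1 has 50% (7,436/14,950) and 2/2 has 41% (6,084/14,950). At r = 0.5 the two commoner splits leave the error rate close to nominal. A reader might take 20% as the expected false-positive rate. It needs both the rarest split and a perfect link between stopping and outcome. What remains is that the arms do different sessions, so a random split cannot be taken for granted.
- **Feasibility.** The past tense and final counts suggest that week 6 has passed, so recall may be impossible. This stands and shapes the fix.

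**Conclusion.** The point holds as a gap in outcome collection and analysis. The post tests are linked to completing the course, four dropouts are reported, and nothing says whether an allocated patient who stopped was measured or in which group that patient was analysed. A completers-only comparison is the likely reading, but it is not established.

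The consequence depends on the dropouts having come after the lottery, on their split by arm, and on how strongly stopping is linked to outcome. The documents give none of these. At a moderate link the effect runs from no average bias to about a quarter of an SD, with false positives between about 5% and 8%. The larger figures at r = 1 are upper bounds. Arm sizes, alpha and the normal outcome model are also assumptions. This should be corrected or clarified before the between-arm results are read as a comparison of the groups as randomised.

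**What to change.** **If patients can still be measured**, replace the sentence on post tests in the Data Collection Procedure with: *Post tests (echocardiography, lipid profile, MacNew) are done 6 weeks after the first scheduled session in every patient allocated by lottery, whatever number of sessions was attended, unless the patient withdraws consent to follow-up.* Add to the Data Analysis Procedure that each patient is analysed in the allocated arm.

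**If data collection is finished**, include any dropout who was measured in the allocated arm. If none was, describe the result as a completers-only comparison. In either case:

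- report the dropouts by arm, timing (before or after the lottery) and reason, with their baseline ejection fraction, lipid and MacNew values;
- reconcile the statement in the Data Analysis Procedure that all patients were assessed with the Data Collection Procedure and its counts of 26, 26 and 4.

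**Cost.** The first route takes a sentence in each section and tests for about four patients, of a kind already planned for everyone. Including patients who stopped may dilute the observed effect slightly, and some may not attend. The second route needs only records that the trial should already hold.

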### **TREATMENT PROTOCOL:**

Patients in both group received standard treatment that is Aerobic Interval training whereas patients in interventional group was given Resistance Interval Training as well.

Before initiation of treatment protocol vitals (HR, BP, RR and SPO2) will be recorded. Treatment of both groups will start with 3-5 minutes of warm up that includes breathing exercises and stretching of major large muscles. Exercise will be performed at 60-80 % of intensity calculated by karvonen formula. Throughout training monitoring will be done.

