### **CONTROL GROUP:**

Patients in control group will perform 6 minutes of cycling followed by 3 minutes of pause and again 6 minutes of cycling followed by 3 minutes of pause and finally 6 minutes of treadmill followed by 3 minutes of rest.

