### **INTEREVNTIONAL GROUP:**

Patients in Interventional group in first set will perform 3 minute of cycling ,1 set of hand grippers 1.5 to 2.5 lbs (10 to 12 reps) and 1 set of biceps resistive exercises 1 Kg to 3 kg (10 to 12 reps) followed by 3minute of pause. In second set patient will perform 3 minutes of stationary cycling , 1 set of quadriceps resistive exercises 1 to 3 Kg (10 to 12 reps) again followed by 3 minutes of pause and in third set patient will perform 3 minutes of treadmill walk at 1.5 to 4 speed, and 1 set of standing ankle pumps (10 to 12 reps).

Patients in both groups will perform cool down exercises that include again breathing exercises, stretching and active exercises. Post exercise vitals will be recorded in both groups.

Figure 3: Patient performing treadmill as a part of treatment protocol

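### The treatment section describes resistance added to standard aerobic training, but the sessions prescribe 9 aerobic minutes against 18, so the trial compares two packages and does not test an add-on

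*Combined protocol and SAP*

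**What the plan says.** The Treatment Protocol section introduces the two arms with one sentence: "Patients in both group received standard treatment that is Aerobic Interval training whereas patients in interventional group was given Resistance Interval Training as well". The sections after it set out each session.

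- **Control Group:** "Patients in control group will perform 6 minutes of cycling followed by 3 minutes of pause and again 6 minutes of cycling", then, after another pause, "finally 6 minutes of treadmill followed by 3 minutes of rest".
- **Interventional Group, first set:** "Patients in Interventional group in first set will perform 3 minute of cycling", with one set each of hand grippers and biceps work.
- **Interventional Group, second set:** "In second set patient will perform 3 minutes of stationary cycling", with one set of quadriceps work.
- **Interventional Group, third set:** "in third set patient will perform 3 minutes of treadmill walk at 1.5 to 4 speed, and 1 set of standing ankle pumps". No weight is given for the ankle pumps.

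The Data Collection Procedure section also describes the arms: "Patients in control group were given standard aerobic interval treatment while patient in experimental group was given aerobic plus resistance interval treatment". It gives 18 exercise days (three a week for six weeks) and describes progression by speed and weight: "Patient speed was increased gradually from first to six weeks depending on each patient target heart rate". Repetitions stay fixed.

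**The concern.** The Treatment Protocol sentence names aerobic interval training as the standard that both arms received and says resistance came on top. The Control Group section is the only full specification of that standard, and the interventional session contains half its aerobic minutes. The arms therefore differ in two prescribed components: whether resistance work is present, and how long the aerobic work lasts. Two arms cannot separate two components.

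What is at stake is how a result on echocardiography, lipids or the MacNew questionnaire would be read. Someone relying on the introductory sentence would take a difference as the benefit of adding resistance, and no difference as evidence that adding it does nothing. Neither follows. A null result, for example, could arise from a resistance benefit offset by less aerobic time. For a rehabilitation service, adding resistance to the usual session and running a mixed session with half the aerobic time are different instructions.

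**Working it through.** The plan states no total of aerobic minutes, so there is no figure to reproduce. The check sums the prescribed bouts.

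| Bout | Control Group | Interventional Group |
|---|---|---|
| 1, cycling | 6 min | 3 min, plus hand grippers and biceps (1 set each) |
| 2, cycling | 6 min | 3 min, plus quadriceps (1 set) |
| 3, treadmill | 6 min | 3 min, plus ankle pumps (1 set) |
| **Aerobic total per session** | **18 min** | **9 min** |

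**Sessions.** 3 per week × 6 weeks = 18, which agrees with the count in Data Collection Procedure.

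**Course totals.** Control: 18 × 18 = 324 min. Interventional: 9 × 18 = 162 min. Ratio: 162 / 324 = 0.50. Every bout is halved, with the same type of exercise in the same order.

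**Work in the interventional group only, per session.** Three weighted sets × 10 to 12 = 30 to 36 repetitions, plus one ankle-pump set of 10 to 12 repetitions.

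**Does anything else restore the 9 minutes?**

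- Warm-up: its length differs between Data Collection Procedure (15 minutes) and Treatment Protocol (3 to 5 minutes), but neither section separates the groups.
- Cool-down: the same content for both groups.
- Progression: by speed and weight. No bout is lengthened.
- Intensity: 60-80% by the Karvonen formula, with no group difference. This sets intensity, not duration.

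**Could the interventional session have been done on top of the control session?** That would give 18 + 9 = 27 aerobic minutes per session, or 27 × 18 = 486 over the course. The arms would still be unequal, and the parallel three-bout layout does not suggest it.

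**Could the sets make up the time?** Set duration is not given. Assuming 30 to 90 seconds per set, four sets take 2 to 6 minutes, so active time would be 9 + 2 = 11 to 9 + 6 = 15 minutes against 18. Filling 9 minutes would need 9 / 4 = 2.25 minutes per set. Whatever the duration, that time is resistance or ankle-pump work and is not part of the aerobic bouts.

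**The case against.** The best defence is that the sentence labels the types of exercise and makes no promise about dose. It gives no minutes, the interventional group does perform aerobic intervals, and the full prescriptions follow at once. A mixed programme with shorter aerobic bouts is a legitimate design. The text available for review states no objective, hypothesis or conclusion about unchanged aerobic training, so nothing has been shown to be misattributed.

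Much of this stands. The design needs no defence, nothing is concealed, and the point is a risk of misreading. What does not stand is the label reading. Calling aerobic interval training the standard treatment of both groups, with resistance as an extra, most naturally means the same aerobic programme in each arm, and the prescriptions contradict that. No section states an intention to substitute one for the other or to match session time.

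Three further objections also hold:

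- The Data Collection Procedure sentence attaches the word standard to the control arm only. It is compatible with a mixed programme and is not in error.
- A reader might infer that resistance replaced aerobic work minute for minute. Without set durations, that cannot be shown.
- A reader might infer that the cardiovascular stimulus was halved. Both arms share a target heart rate, the sets fall within the same intervals, and time at target is not reported. Only the prescribed minutes are known to be halved.

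**Conclusion.** The point holds as a contradiction between the Treatment Protocol sentence and the two prescriptions below it. Prescribed aerobic time is 9 against 18 minutes per session, a shortfall of 9 minutes per session and 324 − 162 = 162 minutes over the course, and four sets appear in one arm only. A between-group result belongs to the whole package and cannot be credited to resistance added to standard training.

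It would be tempting to go further and call the comparison confounded or biased against the interventional arm. The documents do not support that. Allocation was by lottery, so the comparison of the packages as given is valid, and neither the direction nor the size of any effect of the shorter aerobic time can be stated.

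The minutes are exact as prescribed. The conclusion assumes that the Control Group and Interventional Group sections describe the sessions actually delivered. It needs no assumption about set duration or achieved heart rate. It should be fixed, because it changes which clinical question the trial can be said to answer.

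**What to change.** First check the session records against the two prescriptions.

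- **If the prescriptions reflect delivery:** reword the Treatment Protocol sentence to say that the interventional group had 9 prescribed aerobic minutes per session, against 18 in the control group, plus three resistance sets and one set of ankle pumps. Avoid wording that says the sets took the place of the other 9 minutes. Limit any conclusion to mixed aerobic-resistance versus aerobic-only interval training.
- **If the prescriptions misreport delivery:** correct them to the sessions that patients actually performed, not to the intended label. Then restate the contrast to match.

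The Data Collection Procedure sentence can stay as it is.

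The cost is one sentence and the scope of the conclusion. No new outcome data and no change of analysis are needed. The downside is the narrower claim: on the prescriptions as written, the trial cannot be presented as a test of adding resistance to unchanged aerobic training.

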### **CONTROL GROUP:**

Patients in control group will perform 6 minutes of cycling followed by 3 minutes of pause and again 6 minutes of cycling followed by 3 minutes of pause and finally 6 minutes of treadmill followed by 3 minutes of rest.

